### **Interventions and Interactions**

**Participants.** We will enroll 48 men and women 18-75 years old with CLBP that may or may not have a history of current prescription opioid use (>3 months) for the treatment of pain. Participants will be recruited through the community along with WFU clinics. Patients that have previously agreed to be contacted for research and have current chronic pain will be referred to the study. Our prior history with targeted enrollment (See Significance) indicates this is feasible within 20 months, leading to full completion by 22 months. **Exclusion criteria:** Typical MRI and TMS exclusionary criteria, including metal above the neck or implanted in the body, use of prescription medications that lower seizure threshold, a history of seizures or traumatic brain injury, pregnancy or trying to become pregnant, current substance use or dependence (other than opioids and nicotine), history of seizure disorder, and claustrophobia. Participants will provide written informed consent following explanation of the study.

[figure not shown]
### **General Methods**

**Screening Visit – Consent.** Participants will receive a series of assessments designed to evaluate opioid dependence, psychiatric conditions, chronic pain and mood. These include the MINI International Neuropsychiatric Interview (46), Brief Pain Inventory (47), Timeline Followback (48), Beck's Depression Inventory II (49), State-Trait Anxiety Inventory (50), the Pittsburgh Sleep Quality Index (PSQI), the Barratt Impulsiveness Scale (BIS), and Profile of Mood States (51). Data will be collected using REDCap™, and entered directly into the online portal to ensure security and prevent data loss.

During COVID-19, study personnel will interact with participant via the Wake Forest Baptist Health (WFBH) institutional WebEx videoconference software as necessary. Participants will remotely sign and date the informed consent document.

**Intervention – MRI Visits 1-3.** Following enrollment, participants will meet the study personnel for Assessment & MRI Scanning (details below). The procedures at MRI Visit 1 will be repeated at MRI Visit 2 (after 12 days of rTMS), and at MRI Visit 3 (after 16 days of rTMS).

**Strategy 2: iTBS to the MC.** This protocol is identical to that used for the DPFc explained above, with the exception of using 90% RMT rather than 110% RMT.

During each real and sham TBS session each day the amplifier output will be escalated (“ramping” in 5% increments over 30 seconds) to enhance tolerability. The time between the end of the TBS procedures and the beginning of the behavioral assessments will be compiled and used as covariates in subsequent analyses.

**TMS ACTIVE SHAM system:** The MagVenture MagPro system has an integrated, active sham which passes current through two surface electrodes placed on the scalp. The electrodes will be placed on the left frontalis muscle for all sessions. A patient ID card will randomize participants to receive either real or sham stimulation. This system maintains blinding by a gyroscope in the coil which indicates to the clinical staff whether the coil should be rotated up or down for this participant once the card is entered into the machine. One side of the coil is active, the other is sham. To assess the integrity of the blind (active sham) a questionnaire will be given to both the patients and to the research staff at day 1, 6, 10 to evaluate their opinion on whether they received real or sham, their level of confidence (Likert scale 1-10), and their rationale (text entry).

**Assessments:** The primary dependent measures will be extracted from the Quantitative Sensory Testing for pain thresholds. Other assessments include: Brief Pain Inventory (BPI), the pain craving form, and subjective pain rating scales, delivered before and after TMS. Participants will also complete the Beck Depression Inventory (BDI-II), the Profile of Mood States (POMS), the Pittsburgh Sleep Quality Index (PSQI), the State-Trait Anxiety Inventory (STAI), and Barratt Impulsiveness Scale (BIS), which assesses anxiety and depression measures. Though these are not primary outcomes, the results will be used in post-hoc analyses of the data. All surveys will be filled out by the patient on tablet computers (Apple iPad/Microsoft Surface) and data entry will be done directly via Redcap Software.

**MRI scanning:** The MRI scanning session will last 30 minutes and will contain: 1) a high resolution anatomical image (T1-weighted MPAGE (TR 1.9 sec, TE 2.26 ms, 2x GRAPPA, 1 mm isotropic)), 2) resting state functional connectivity (TA 7 minutes, voxel size: 2.5 x 2.5 x 2.5, TR = 2.6 s, TE = 25 ms, flip angle = 60°, FOV = 224 mm x 224 mm, matrix size = 64 x 64), For each of the above strategies (Active rTMS or Active Sham) we will explore a series of SubAims designed to quantify the effects of rTMS on subjective pain, quantitative sensory testing, and brain reactivity to pain.

**SubAim 1- Evaluating Pain using Clinical Assessments and Quantitative Sensory Testing (QST):** Using the Medoc ATS pressure algometer (Medoc Ltd Advanced Medical Systems, Ramat Yishai, Israel), 3 primary outputs will be compiled for each individual via the method of limits (54): sensory threshold, pain threshold, tolerance threshold. The algometer has a rubber tip that will be pressed into the right forearm for the procedure. Participants will indicate when they first detect the pressure change (sensory threshold), when it becomes painful (pain threshold), and when they can no longer tolerate the stimuli (tolerance threshold). When participants indicate tolerance, the operator will release the algometer. QST will be performed at the following timepoints: for the first TMS visit, the QST will be administered prior to the first TMS session and immediately following the second TMS session; for the remainder of the TMS visits and follow-up visits, QST will be performed prior to the first TMS session at each visit. The acute changes for TMS visit 1 will give one measure for acute pain changes pre/post TMS. **Pain**

**Questionnaire.** In order to evaluate current levels of pain, we will ask participants to rate their current level of pain and discomfort (scale, 0 through 10), each time the participant comes in (Table 1). On days where the individual receives rTMS, they will fill out this assessment between each TMS session. **Pain and Craving Questionnaire:** In addition to the Pain Questionnaire above, participants will also rate their urge to use a pain reliever (Scale 0 – 10) and the amount they would be willing to pay for a pain reliever (in US Dollars). This questionnaire will be used at the same time during each intervention visit as the Pain Questionnaire (Table 2).

**SubAim 2: Evaluating Pain using Neuroimaging Data** At baseline we expect that people with chronic pain will have elevated activations in the Pain Network. This will be analyzed through the resting state connectivity network. Following sham stimulation, we do not anticipate a significant reduction of this response. Based on prior studies by our group in non-opiate dependent individuals, following LTP-like stimulation of the DPFC, we expect a significant amplification of the DPFC (% BOLD signal change), and a reduction of the Pain Network (dACC, anterior insula) reflecting the increased influence of executive processes. MC TMS however will likely not have as large of an effect on ECN engagement during the instruction to Control the pain.

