### **Sample Size**

A power estimate for Aim 1 and 2 was prepared using an original fMRI dataset previously collected in our laboratory (8). In this experiment, 18 healthy controls performed the same fMRI pain paradigm as the present study before and after a single session of 10 Hz rTMS. Mean parameter estimates for the “heat pain vs. rest” condition were extracted from several *a priori* regions of interest. These data yielded an effect size which ranged from 0.70 (thalamus) to 1.08 (insula) (n=15 yields 80% power using a two-sided p<0.05). Allowing for a 10% dropout rate after the screening visit, and up to a 20% dropout rate at the end of the Treatment phase (Week 4), as well as a 10% data loss rate for MRI (Aim 2) due to individuals with excessive head motion in the MRI scanner, screening 58 individuals should lead to complete data from 48 individuals (16 real DPFC, 16 real MC, 16 sham (50% at each site)). Randomization will be handled by a Latin Square design with replacement will be used to ensure even enrollment across groups with replacement. All individuals will be enrolled at WFUHS. Data analysis and quality assessment will be ongoing.

Due to several COVID related factors, including challenges with scheduling and hesitation that participants may have wearing a mask in the MRI scanner, some participants will not receive the MRI

portion of this experiment. This will not affect our total enrollment goals, nor compromise the scientific integrity of this study. Moreover, it will lower the risk associated with MRIs to these participants.

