### **Outcome Measure(s)**

- A. Quantitative Sensory Testing.** The QST pain assessment produces 3 output variables: sensory threshold, pain threshold, tolerance threshold (all expressed in kiloPascals). The hypothesis will be tested using a within-subject repeated measures design (time x treatment) wherein time is the repeated variable and Real or Placebo TMS is the grouping variable. Given that the purpose of this pilot study is to develop effect sizes for a subsequent R01, we will derive least-squares means effect sizes of this strategy on these thresholds. Secondary analyses will evaluate the relationship between QST levels and the neural response to pain, as well as the relationship between QST values and evoked cortical responses. Integrating these measures together will provide a more complete picture of how cortical activity is able to modulate the pain response.
- B. Questionnaires and Evaluations.** The Opiate Pain inventory produces 4 output variables of interest: level of discomfort, level of pain, urge to use opiates, amount willing to pay for an opiate. The hypotheses for the Aims will be tested using a within-subject repeated measures design (time x treatment) wherein time is the repeated variable and Real or Placebo TMS is the grouping variable. Given that the purpose of this pilot study is to develop effect sizes for a subsequent R01, we will derive least-squares means effect sizes of our research strategy on these 4 variables, to determine the unique contributions of this intervention.

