**Expected (and alternative) Outcomes:**

- A. **Quantitative Pain Testing.** Based on our pilot data, we expect an interaction between treatment (Real DPFC or MC TMS vs. Sham) and time (Before vs. After rTMS) on the painfulness QST measure but no effect on sensory or tolerance levels. Alternative outcomes: It is possible that individuals will experience a small level of acute pain relief from their normal regimen of medication. We will be collecting information on opiate dose and timing at each visit to be used as potential covariates. Further, there is the possibility that pain tolerance will rise, possibly also reflecting improvements in executive function.
- B. **Qualitative Pain Assessment.** We expect reductions in pain and discomfort when comparing active vs sham. However, based on prior data in opiate dependent individuals, we expect the effect size of DPFC rTMS in to improve measures of Control but not measures of mood, whereas MC will have a larger effect on mood.
- C. **Neuroimaging.** At baseline we expect that there will be elevated activations in the Pain Network in individuals with chronic pain. Following sham stimulation, we do not anticipate a significant reduction of this response. Based on prior studies by our group in non-opiate dependent individuals, following LTP-like stimulation of the DPFC, we expect a significant amplification of the DPFC (% BOLD signal change), and a reduction of the Pain Network (dACC, anterior insula) reflecting the increased influence of executive processes.

Alternative outcomes: Though pilot data suggest that a single treatment will acutely reduce self-reported pain, it is possible that the neural circuits in opiate dependent individuals do not have the same ‘plasticity potential’ as in controls. If we fail to replicate prior work showing DPFC activation, this could reflect executive deficits (58), suggesting that the MC TMS will be more efficacious.

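### All three QST thresholds are primary and unranked, although an effect is predicted on only one; the chance of a false-positive primary QST test is about 8–14%, or 15–25% if each site is tested against sham

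*Combined protocol and SAP*

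**What the plan says.** Four places bear on this.

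- **General Methods, Assessments.** "The primary dependent measures will be extracted from the Quantitative Sensory Testing for pain thresholds". The noun is plural and no single threshold is named. The mood, sleep and impulsiveness scales are set apart as not primary.
- **General Methods, SubAim 1.** "3 primary outputs will be compiled for each individual via the method of limits (54): sensory threshold, pain threshold, tolerance threshold".
- **Outcome Measure(s), item A.** The same three thresholds are listed again. The hypothesis is to be tested in a time-by-treatment repeated-measures model with real or placebo stimulation as the grouping factor, and "we will derive least-squares means effect sizes of this strategy on these thresholds". None is ranked above the others.
- **Expected (and alternative) Outcomes, item A.** A treatment-by-time interaction is expected "on the painfulness QST measure but no effect on sensory or tolerance levels". Under alternative outcomes, "there is the possibility that pain tolerance will rise, possibly also reflecting improvements in executive function".

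The Analytical Plan adds general methods but no hierarchy, no significance level for QST and no multiplicity adjustment. The number of contrasts per threshold is also open. Item A of Outcome Measure(s) describes one real-or-placebo factor, whereas Aims 1 and 2, and the Exploratory Analysis paragraph, treat the prefrontal (DPFC) and motor (MC) sites separately against sham.

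**The concern.** Two of the three thresholds called primary are predicted not to move, and for one of those two an explanation is already supplied in case it does. The plan does not say which threshold decides the QST hypothesis. If all three are tested at the nominal level, the chance of some false-positive primary result exceeds 5%.

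The stated purpose, to develop effect sizes for a later R01, does not remove the problem. With no threshold named in advance, nothing prevents the largest of several estimates from being the one carried forward, and an estimate picked for its size is biased upwards. The plan does not say that this will be done; it simply leaves the choice open.

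**Working it through.** **The plan's own figure.** The only stated significance level is in Sample Size: "n=15 yields 80% power using a two-sided p<0.05", next to fMRI effect sizes of 0.70 to 1.08. A two-sample t-test with 15 per arm and d = 1.08 gives 81.5% power, so the figure reproduces at the top of the range. At d = 0.70 a paired t-test with n = 15 gives 71%. This calculation concerns fMRI. It supplies the 0.05 assumed below and has no other bearing on QST.

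**Inputs**

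- Thresholds: 3 (General Methods, SubAim 1).
- Arms: 16 DPFC, 16 MC, 16 sham, the sham group shared (Sample Size).
- Contrasts per threshold: 1 (Outcome Measure(s), item A) or 2 (Aims 1 and 2; Exploratory Analysis).
- Level of each test: two-sided 0.05. *Assumption*, because no level is given for QST.
- Correlation ρ between thresholds: not given. *Assumption*, equal for all pairs, range 0 to 0.9.
- One test per threshold and contrast, on a single change score, at one final analysis. *Assumption*.

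**Independent tests.** P(at least one) = 1 − (1 − 0.05)^k.

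- k = 3: 1 − 0.95³ = 14.3%.
- k = 6: 1 − 0.95⁶ = 26.5%.

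**Allowing for correlation.** Two contrasts that share one sham group of equal size are correlated 0.5. The error rates were simulated with no effect anywhere, 16 per arm and pooled-variance t-tests.

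| ρ | 3 tests: real vs sham | 6 tests: each site vs sham |
|---|---|---|
| 0 | 14.2% | 24.6% |
| 0.3 | 13.7% | 23.4% |
| 0.5 | 12.7% | 21.9% |
| 0.7 | 11.1% | 19.3% |
| 0.9 | 8.3% | 14.9% |

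A three-group test with 2 degrees of freedom per threshold gives nearly the same as the first column (14.3% down to 8.7%).

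**Narrower question.** The table counts significant falls as well as rises, and it counts the sensory threshold, where no effect is expected. Counting only a significant *rise* in the *pain or tolerance* threshold, over ρ = 0 to 0.9:

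- each site vs sham: 8.9% down to about 6% (8.0% at ρ = 0.5);
- pooled real vs sham: about 5% down to about 4% (4.5% at ρ = 0.5).

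**With one threshold named.** One pooled test: 5%. Two sites against the shared sham, each at 0.05: 9.1%. Two sites with Dunnett's adjustment: 5%.

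**Picking the largest.** With no true effect, the expected largest of the six standardised differences is roughly 0.24 to 0.39 for ρ = 0.9 to 0.3.

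**The case against.** The strongest reply is that this is a pilot whose declared aim is estimation, that effect sizes are to be derived for all three thresholds, and that the protocol has in effect already named its target by predicting an effect on the pain threshold and none on the other two. On this view, primary outputs in SubAim 1 means no more than what the device produces, and the remark on tolerance is discussion rather than a success criterion.

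Much of this stands. Nothing says that a tolerance-only result would meet the hypothesis. The prediction in Expected Outcomes is a real pre-statement, and an expected-null sensory threshold can still serve as a check whatever it is called. The reply does not close the gap, however. The Assessments paragraph makes QST primary without choosing a threshold, the outcome section says that the hypothesis will be tested as well as estimated, and the prediction is never turned into a rule for analysis.

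Two stronger readings are tempting, and the documents support neither.

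- A reader might infer that calling three thresholds primary makes a false positive a 1-in-5 event. Three thresholds alone give at most 14.3%, about 1 in 7. Figures near 20% also need separate tests of each site and an assumed correlation of about 0.5 to 0.7.
- A reader might infer that almost any pattern of results could be claimed as support. A large part of the error comes from falls in threshold or from the sensory threshold, neither of which the protocol treats as support.

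**Conclusion.** The point holds in a limited form. The plan makes three QST thresholds primary and leaves them unranked, against its own prediction. The chance of at least one false-positive primary QST test is about 8–14% under the single real-versus-placebo comparison, and about 15–25% if DPFC and MC are each tested against the shared sham, the reading suggested by Aims 1 and 2. The risk of a false result resembling the stated expectations is about 4–5% and 6–9% respectively.

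These figures rest on an assumed level of 0.05 per test, an assumed correlation of 0 to 0.9, and one test per threshold and contrast at a single final analysis. The text does not settle which set of contrasts is meant. The remedy is cheap and follows the sponsor's own hypothesis, so it should be adopted before the data are analysed.

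**What to change.** - In General Methods (Assessments and SubAim 1) and Outcome Measure(s), item A, name the pain threshold as the single primary QST outcome, as Expected Outcomes predicts. Make tolerance secondary and report the sensory threshold as an expected-null check.
- State that the pain-threshold effect, not the largest of the three, goes forward to the R01. Still report all three.
- In Outcome Measure(s), item A, state the primary contrast: either pooled real against sham (one test, 5%), or each site against sham (about 9% unadjusted, 5% with Dunnett's adjustment). The second option replaces the real-or-placebo grouping factor with three groups.

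**Cost.** Mostly wording. A tolerance-only effect could no longer be called the primary QST result. Dunnett's adjustment costs some power: with 16 per arm, and borrowing the fMRI effect sizes as an assumption, power per comparison falls from 85% to 78% at d = 1.08 and from 49% to 39% at d = 0.70. The pooled test (32 against 16) would have 93% and 61%, if both sites shared the same effect.

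**Limit.** This controls error within QST only. It does not resolve the statement in Objectives and Exploratory Analysis that the MRI comparison of visits 1 and 2 is primary, nor the analysis at 50% recruitment under Data and Safety Monitoring, for which no adjustment is given.

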### **Outcome Measure(s)**

- A. Quantitative Sensory Testing.** The QST pain assessment produces 3 output variables: sensory threshold, pain threshold, tolerance threshold (all expressed in kiloPascals). The hypothesis will be tested using a within-subject repeated measures design (time x treatment) wherein time is the repeated variable and Real or Placebo TMS is the grouping variable. Given that the purpose of this pilot study is to develop effect sizes for a subsequent R01, we will derive least-squares means effect sizes of this strategy on these thresholds. Secondary analyses will evaluate the relationship between QST levels and the neural response to pain, as well as the relationship between QST values and evoked cortical responses. Integrating these measures together will provide a more complete picture of how cortical activity is able to modulate the pain response.
- B. Questionnaires and Evaluations.** The Opiate Pain inventory produces 4 output variables of interest: level of discomfort, level of pain, urge to use opiates, amount willing to pay for an opiate. The hypotheses for the Aims will be tested using a within-subject repeated measures design (time x treatment) wherein time is the repeated variable and Real or Placebo TMS is the grouping variable. Given that the purpose of this pilot study is to develop effect sizes for a subsequent R01, we will derive least-squares means effect sizes of our research strategy on these 4 variables, to determine the unique contributions of this intervention.
- C. Neuroimaging Data (Aim 2):** Immediately following acquisition, functional structural data will be uploaded to a secure data server and converted to NIfTI format. All preprocessing and analyses will be performed using Statistical Parametric Mapping 12 (SPM12) in Matlab 2013 (Mathworks). Functional data will be corrected for magnetic field inhomogeneity and realigned (rigid-body, minimizing least squares differences) to the first image in the time series (Realign: Estimate and Unwarp). Non-linear deformations required for standard space normalization will be derived from each participant's anatomical image via a unified segmentation approach (Segment). After the mean realigned and unwarped functional image is coregistered to the skull stripped anatomical image (Coreg: Estimate) forward deformations (subject space to MNI standard space) will be applied (Normalise: Write). Finally, the data will be smoothed by an 8 mm full width half maximum Gaussian smoothing kernel (Smooth). Within-subject and between-group modeling. Data will be analyzed at the subject level using multivariate pattern analysis (Wager et al 2013 “An fMRI-Based Neurologic Signature of Physical Pain” new England Journal of Medicine). The six motion parameters (translations and rotations) will be included in the design matrices as covariates to account for non-task signal.

Resting State Connectivity will be measured to compare MRI scan 1 to scan 2 – immediately after the treatment. MRI scan 3 will also be compared to these scans to see if there is a sustainable reduction in pain activity between these networks. Additionally factor analysis will be used to investigate the durability of the effects of each strategy on functional connectivity in each of the 3 Core networks (SN, ECN, DMN) using factor analysis longitudinally. **Covariates:** As an exploratory analysis we will also quantify the impact of several covariates which have previously been documented to affect the brain response to pain and pain thresholds (sex, Becks Depression Inventory score, length of time using chronic opiates). Although all participants will have taken their daily dose of opiates, which has a stable pharmacokinetic profile, we will also consider time since last dose.

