**Exploratory Analysis:** We will evaluate if there are rate-dependent effects between baseline SN connectivity with the ECN and DMN and the efficacy of each TMS strategy on subjective pain. Data will be analyzed by using multivariate pattern analysis (MVPA) (2014). While the primary outcomes will be MRI V1 vs V2, we will also examine the relative ‘durability’ of the effects on pain by comparing the MRI data at the 1 month follow up between and within groups with factor analysis. **Integration of Brain based and Behavioral Based Outcomes with Gender and other Demographic Variables:** Finally, we will compare the relative efficacy of these two types of TMS using the behavioral and neuroimaging measures. Specifically, we will determine the effect sizes for DPFC and MC (relative to sham) stimulation on reducing the 1) the neural and 2) behavioral responses to pain, as well as 3) changes in clinical assessment metrics (see Approach). We will investigate the role of baseline cortical responsiveness on the pain response, as well as how changes in that evoked response are related to changes in both pain and craving measures. This will be specifically addressed as a factor of gender as

well, given that there are established differences in sensitivity to pain and prevalence of opiate dependence between men and women.

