#### **Risks associated with MRI scanning (minimal risk):**

1. The major potential risks for MRI are all subsumed under the risks for TMS and primarily include risks to individuals who have metallic implants, pacemakers, or pregnant women. These individuals will be excluded from the study.
2. Participants may feel restless or uncomfortable when lying in the MRI scanner.

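### The resting-state scans get a task-style motion step, with no motion limit and no comparison of motion by arm, so residual head motion could bias the scan 1 versus scan 2 connectivity contrast in either direction.

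*Combined protocol and SAP*

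**What the plan says.** General Methods (MRI scanning) lists two acquisitions: an anatomical image and "resting state functional connectivity (TA 7 minutes", at a repetition time of 2.6 s. No task run is listed, and SubAim 2 says that the imaging question will be examined through resting-state connectivity.

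Outcome Measure(s), part C, describes preprocessing step by step. Functional images are "corrected for magnetic field inhomogeneity and realigned (rigid-body, minimizing least squares differences) to the first image in the time series (Realign: Estimate and Unwarp"), then normalised and smoothed with an 8 mm kernel. After the sentence on multivariate pattern analysis comes the nuisance model: "The six motion parameters (translations and rotations) will be included in the design matrices as covariates to account for non-task signal". The next paragraph gives the contrast: "Resting State Connectivity will be measured to compare MRI scan 1 to scan 2". The covariates named there are sex, depression score, duration of opiate use and time since last dose. None is a measure of head motion.

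Sample Size allows for a "10% data loss rate for MRI (Aim 2) due to individuals with excessive head motion in the MRI scanner", without saying how motion is measured, what counts as excessive, or that the rule is applied blind to arm.

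On the status of the contrast, the exploratory paragraph under Expected (and alternative) Outcomes says: "While the primary outcomes will be MRI V1 vs V2". Objectives says the same, although the Assessments paragraph takes the primary measures from quantitative sensory testing.

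**The concern.** Connectivity is a correlation between the signals of brain regions. Head motion adds signal that regions share, or disrupts signal that they share, so motion left in the data changes the outcome itself. In a task analysis, motion regressors clean up the background around a known stimulus. At rest there is no stimulus, and everything not removed goes into the correlation.

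The trial's own hypothesis gives motion a route to differ by arm. Expected (and alternative) Outcomes predicts less pain and discomfort on active TMS than on sham. The MRI risk section notes: "Participants may feel restless or uncomfortable when lying in the MRI scanner". If discomfort affects how still a participant lies, and discomfort falls more on active treatment, motion at scan 2 could differ between arms, and the sham arm would not cancel it. Within-group comparisons across scans are exposed to any change in motion over time, even one equal across arms.

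The stake is mainly the neural effect sizes relative to sham, which the plan wants as the basis for a larger trial.

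**Working it through.** **1. What is scanned.** 7 min × 60 = 420 s; 420 / 2.6 = 161.5, so about 161 volumes per scan, all at rest.

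**2. What the plan does about motion.**

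| Step | In the plan? |
|---|---|
| Realignment and unwarping | Yes (Outcome Measure(s), C) |
| Six realignment regressors | Yes (same section), worded for a task design |
| Exclusion for excessive motion | Foreseen at 10% (Sample Size); no metric or limit |
| Expanded motion terms | Not named |
| White-matter and CSF signals | Not named |
| Temporal filter | Not named |
| Displacement measure, volume censoring | Not named |
| Motion covariate, or motion by arm and scan | Not named |

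The section is detailed enough to name software modules and the kernel width, so the missing steps are more than detail left to a manual.

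**3. Does the quoted sentence govern the resting data?** It sits beside the pattern-analysis sentence, and the resting-state paragraph that follows states no nuisance model of its own. If the sentence applies to the resting data, six regressors are the whole nuisance model. If it does not, the resting data have none stated. The gap exists either way.

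**4. Size.** The plan gives no figure for motion beyond the 10% allowance, so there is nothing to reproduce and the bias cannot be calculated. An illustration shows only how it would scale.

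- D: between-arm difference in change of motion, in SD units (assumed 0.2 to 0.8).
- r: correlation of change in motion with change in connectivity that remains after the planned steps (assumed 0.1 to 0.5, of either sign).
- Spurious standardised difference: b = r × D.
- Two-sided 5% t-test, n = 16 per arm (Sample Size), 30 degrees of freedom, noncentrality b × √(n/2) = b × √8.

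| r | D | b | Noncentrality | False-positive rate |
|---|---|---|---|---|
| any | 0 | 0 | 0 | 5.0% |
| 0.1 | 0.2 | 0.02 | 0.06 | 5.0% |
| 0.3 | 0.5 | 0.15 | 0.42 | 7.0% |
| 0.5 | 0.5 | 0.25 | 0.71 | 10.5% |
| 0.5 | 0.8 | 0.40 | 1.13 | 19.5% |

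A negative r gives the same rates with the bias reversed, and it could then hide a real effect. If either r or D is zero there is no bias. Sample Size also says that some participants will not be scanned, so 16 per arm is an upper figure for imaging.

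**The case against.** The strongest reply is that this is a gap in specification and not a demonstrated bias. Much of that stands.

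- A reader might infer that six regressors are the only protection. They are not: the plan also realigns and unwarps, and it foresees excluding scans with gross motion. These steps reduce motion artefact, but they do not deal with smaller differences among the scans that are kept.
- A reader might infer that a change in motion will show up as a benefit of TMS. That needs both a change in motion that differs by arm and a residual link between motion and connectivity. The documents give data on neither, and the sign is open.
- The MRI risk section is a general statement about discomfort. It does not say that back-pain patients move in the scanner or that movement changes with treatment. That link is an inference.
- Setting an assumed bias against the smallest planning effect (0.70) would mislead. That figure is an activation estimate from a heat-pain task in healthy controls after one session, not a between-arm difference in connectivity.
- The trial is double-blind, so nothing shows that exclusions would be made with knowledge of the arm. If treatment changes motion, even a fixed limit may exclude unequally by arm.
- Motion after treatment may itself follow from treatment, so adjusting for it can remove real effect.
- This is a pilot, and its sections disagree on whether imaging is primary.

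What does not stand is the suggestion that the stated pipeline is adequate. Followed as written, it leaves residual motion unaddressed in a contrast that two sections call primary.

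**Conclusion.** The point holds as a weakness of the analysis plan that should be put right. Motion handling in the resting-state data consists of realignment and unwarping, six regressors worded for a task, and an exclusion without a limit. Nothing would show whether motion differs by arm or scan. Residual motion could bias the scan 1 versus scan 2 connectivity contrast in either direction.

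The size is unknown. The illustrative 0.02 to 0.40 SD, and false-positive rates of 5.0% to 19.5%, rest wholly on assumed r and D and should not be read as estimates. The documents do not support saying that the artefact will occur or that it favours TMS.

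**What to change.** 1. In Outcome Measure(s), part C, replace the task-style nuisance step with one written for rest: an expanded motion set (for example 24 terms), white-matter and CSF signals, and a temporal filter.
2. Name framewise displacement as the motion measure. Fix a limit for censoring volumes and a minimum number of retained volumes out of about 161. Do so before unblinding, and before the analysis planned at half recruitment if that uses arm codes.
3. Use the same rule, applied blind to arm, as the exclusion foreseen in Sample Size.
4. Report mean displacement and exclusions by arm and scan.
5. As a sensitivity analysis, show the connectivity contrast with and without adjustment for change in displacement, and state that motion may follow from treatment, so the adjusted result is not automatically the better one.

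No new scans are needed. The cost is some volumes, possibly a few scans, and degrees of freedom: 24 motion terms plus two tissue signals use 26 of about 161, leaving about 135 before filtering and censoring take more. With so short a run, the minimum number of retained volumes should be set with that in mind.
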